When determining whether a complication is valve related this study will use the definitions of the AATS/STS guidelines ⁽²⁾. More specific guidance on these determinations is contained in the following discussions of the various types of complications. In any case, adequate documentation must be supplied to support the contention that a complication generally regarded as valve related is not valve related. Information that pertains to reoperation and death must be recorded on the appropriate sections of CRF4. For death, the cause of death must be established, and an autopsy performed when possible. Attach supporting hospital reports when appropriate. Following completion of the information, the investigator must review, date, and sign the CRF.

Specific Instructions for Completing CRF4 –

The complication form (CRF4) is designed to allow the identification of event type, then to note how each event was treated; what the outcome of the complication was; and what the patient's status at the time of the event was. Death from unrelated causes is also reported on CRF4.

Study valve related reoperation is defined as any operation that repairs, alters or replaces an implanted, study prosthesis, also included are operations that treat other valve related complications but do not involve surgery on this valve, i.e., surgery to resolve a hemorrhagic complication. This category also includes incidental replacement of the prosthesis, e.g., the patient undergoes surgery for a different cardiovascular procedure and the surgeon decides to remove the study valve. Cardiovascular surgical procedures other than repair or replacement of the study valve will also be recorded on the CRF4.

Death will be recorded as cardiac or not, and valve related or not. Valve related deaths include deaths from the following causes:

• thrombosis or thromboembolism;

- endocarditis;
- prosthetic valve dysfunction;
- anticoagulant related hemorrhage;
- hemolysis; and
- congestive heart failure, where documentation of a cause other than the valve cannot be given; and sudden unexplained death without autopsy which can definitely assign other causes than the valve.

Deaths caused by heart failure in patients with advanced myocardial disease and satisfactorily functioning prosthetic valves are not considered valve related. Any death that occurs within 30 days of reoperation for a valve related complication is considered valve related.

Classification of each complication is described in sections that follow.

Thromboembolism

Thromboembolism is defined as any valve thrombosis or embolus exclusive of infection. This includes any new focal or global neurological deficit (transient or permanent), myocardial infarction, prosthetic thrombosis, or peripheral arterial embolus.

A transient neurological event is defined as an abrupt onset of a focal neurological deficit lasting at least one minute but resolving without permanent sequelae.

Acute myocardial infarction (MI) is included as a thromboembolic complication when coronary anatomy was normal at the time of implant and there is no angiographic or other clinical evidence that the MI was due to coronary artery spasm or newly-developed coronary artery disease.

Thrombosis is any thrombus not caused by infection attached to or near an operated valve that occludes part of the blood flow path, interferes with valve function or is sufficiently large to warrant treatment. This is listed as a subcategory of thromboembolism and should be confirmed by imaging study, reoperation (explant) or autopsy. Any patient with confirmed prosthetic valve thrombosis is to be treated with surgery, thrombolysis and/or heparin based on the clinical assessment of the particular patient and on what is considered best and most appropriate treatment for the patient. Clinical judgment can be used to diagnose the presence of thrombosis (lack of normal prosthetic valve sound, prolonged lowered blood pressure, loss of consciousness, cardiovascular shock) if the clinical diagnosis is accompanied by a confirming medical test (echocardiography, cineradiography or angiography).

Thrombi that are secondary to another primary complication; i.e., endocarditis, are recorded but also noted to be a secondary event by stating so in their etiology.

Excluded from the thromboembolism category are:

- Events which occur intraoperatively or within 24 hours of surgery due to myocardial infarction or stroke.
- Any peripheral arterial emboli proven to have originated from another cause, e.g., atrial myxoma.

- Failure to awaken from the surgical procedure.
- Pulmonary emboli.
- Events due to proven ischemic disease of the extremities.

However, if any of these complications occur, document the events anyway on the complication form (CRF4).

For any thromboembolic event it is important to determine the INR of the patient at the time of the event, if possible. Every attempt should be made to do so.

Bleeding Events

Hemorrhage is defined as any episode of internal or external bleeding in patients whether or not they are receiving anticoagulant therapy. This also includes any episode of hemorrhagic tamponade. Any anticoagulants used and INR at the time of hemorrhage should be determined, if possible. These events will be classified as major or minor, and are defined as follows.

• Major: An episode of internal or external bleeding that causes death, stroke, operation, hospitalization, or requires transfusion or pericardiocentesis. Examples include nosebleeds that require outpatient transfusion, cerebral bleeding that results in neurological damage and/or death, and gastrointestinal bleeding that requires hospitalization.

• Minor: All other episodes of internal or external loss of blood. Examples include nosebleeds that do not require transfusion, hematomas due to trauma or surgery that do not require transfusion, and ocular hemorrhage. Bleeding from open traumatic wounds (cuts, abrasions, etc.) are excluded, unless the bleeding goes uncontrolled enough to require intervention that would place the event in the major category.

Prosthetic Valve Endocarditis

Prosthetic valve endocarditis is defined as documented evidence of infection of the prosthesis based on histopathological evidence in a surgical or autopsy specimen and/or customary clinical criteria, including an appropriate combination of positive blood cultures, clinical signs (fever, new/altered cardiac murmurs, splenomegaly, systemic emboli, and immunopathological lesions). The organism(s) involved should be identified whenever possible.

Prosthetic Valve Dysfunction

Prosthetic valve dysfunction is defined as any change in valve performance which results from intrinsic or extrinsic abnormalities that cause stenosis or regurgitation. Prosthetic valve dysfunction can be classified as structural deterioration, nonstructural dysfunction, or paravalvular leak.

a. Structural Valve Deterioration

Structural valve deterioration is any change in function of the prosthesis which results from an intrinsic abnormality that causes stenosis or regurgitation. The diagnosis should be based on an examination of the explanted or damaged valve. Examples include excessive wear, leaflet escape, leaflet fracture, housing crack, leaflet pitting, or sewing ring deterioration. Excluded from this category is structural deterioration which results from endocarditis, paravalvular leak, and thrombosis.

b. Nonstructural Valve Dysfunction

Nonstructural dysfunction of the valve is any change in function of the prosthesis that results in stenosis or regurgitation which is not intrinsic to the valve. Examples include patient-prosthesis mismatch, leaflet entrapment by suture or pannus, paravalvular leak and hemolytic anemia. The diagnosis should be confirmed by examination of the damaged or explanted valve. Events to be excluded are those associated with endocarditis, paravalvular leak, and thrombosis.

c. Paravalvular Leak

Any evidence of leakage of blood around the prosthesis between the sewing ring and native annulus. Diagnosis of paravalvular leak may be obtained from echocardiography; however, definitive diagnosis will be obtained at reoperation, explant, or autopsy. Indicate severity of the leak.

Indicate if the event is secondary to another valve-related complication, e.g., endocarditis, hemolysis, thromboembolism, thrombosis. Such events will be classified as major (required surgical intervention) or minor (does not require surgical intervention).

Hemolytic Anemia

Hemolytic anemia will be recorded as a complication in all cases of anemia that are attributable to the valve, based on usual clinical criteria. Indicate if hemolytic anemia is primary or secondary to another valve related adverse event (e.g., paravalvular leak). Events that are excluded are those due to liver disease, myocardial infarction, or systemic infection, where these causes are confirmed by other clinical evidence.

Hemolysis

On going hemolysis shall be defined by plasma free hemoglobin elevated to 125% of laboratory upper normal and serum lactate dehydrogenase (SLDH) values at greater than twice (200%) the laboratory upper normal unless the cellular source of the SLDH can be determined to be other than the red blood cell as evidenced by isoenzyme elevation of LD3, LD4 or LD5, and/or clinical evidence of recent myocardial infarction. Plasma free hemoglobin, serum haptoglobin, reticulocyte count and SLDH shall be tested whenever hemolysis is suspected in any patient and SLDH isoenzymes shall be fractionated whenever the SLDH test value is above 175% of upper normal.

Unanticipated Valve-Related Event

It is unknown what kind of event would qualify for the use of this form, but it is supplied in case any unknown valve-related complication should arise that does not meet any other defined criterion. Should this happen this event must be reported to the monitor immediately, since it is likely to create immediate regulatory reporting requirements. An occurrence of an unknown negative effect is very serious and must not be left unreported for any length of time.

Congestive Heart Failure

Congestive heart failure will be considered valve related if the event is new and is not continued from a preoperative heart failure condition, and is caused by one of the

following prosthesis-related events: Anticoagulant-related hemorrhage, endocarditis, hemolysis, nonstructural dysfunction, paravalvular leak, structural deterioration, thromboembolism, thrombosis, or reoperation.

The most common causes of non-valve related congestive heart failure are coronary artery disease, hypertension, valvular heart disease (due to a valve other than the study valve), cardiomyopathy, cor pulmonale, congenital heart disease, or unknown causes. When an event is considered not valve related the reasons for that decision must be recorded.

Other Cardiovascular and Pulmonary Complications

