The sponsor will provide case report forms (CRFs) or equivalent electronic data management tools to each principal investigator for the purpose of recording patient data. Assessments will be obtained for the preoperative, operative and discharge period and postoperatively at three and six months and annually to 5 years from the date of implant (Table 2 summarizes the required information at each visit). A follow-up schedule will be provided for each patient based on the implant date.

This protocol is designed to be used within the normal daily practice of each center. No specific instructions other than those in the labeling are given on valve orientation or concomitant drug therapies. This will result in a study that defines complication rates under the various drug therapies.

The investigator will make every attempt to follow the patients and will document the information gathered during the follow-up visits on the CRFs. Follow-up

ata Record
Д
and
Progress
nt
iei
at
Ч
2
Ö
ple
Ta

visits should be made in person; telephone or questionnaire follow-up is not allowed. The patients will be encouraged by the investigator to report any address or telephone number changes. They will also be informed of the importance of returning for scheduled follow-up visits even if they are not having any problems. All dates within the study will be recorded as month/day/year using numeric designators for months. If additional space is needed on any form for any data, the data can be placed on a separate sheet and attached to the form.

The study coordinator should submit preoperative, operative and discharge case report forms within 30 days of the implant. As an exception, these CRFs may be forwarded within 30 days of discharge, if discharge is delayed by patient complication.

All appropriate sections of the CRFs must be filled out accurately and completely. All case reports form must be reviewed, signed and dated by the investigator. The CRFs should be sent expeditiously to the monitor, when completed, and be kept in the patient record notebooks or electronic files provided by the sponsor.

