Where requested, attach additional CRFs or reports.

The Implant Registration Card is included with the valve packaging and is used for tracking valves within the study. It must be completed and returned to the sponsor within 24 hours of the surgery. Sending a copy of the card to the sponsor by facsimile or e-mail is adequate to fulfill this requirement.

There is also a permanent patient record card included in the package labeling. This card is to be completed and given to the patient as a form of permanent medical identification.

Early Postoperative/Discharge Procedures -

The investigator will record the date of the patient's discharge from the hospital and the date of the early follow-up examination on CRF3. The early follow-up exam records the patient's status at the time of discharge or at 30 days, whichever comes first. The patient's NYHA and cardiac rhythm status and any complications will be noted along with the patient's amticoagulation therapy. It is important to record the international normalized ratio (INR) at the time of the exam. Wherever possible this value should be within the therapeutic range required by this protocol in section II C.

At each postoperative assessment, the investigator will need to determine the patient's availability for future follow-up. If any patient needs to be seen at other than a regularly scheduled follow-up visit, the same follow-up information as required at regular times will be documented by the investigator on the follow-up form, and that follow-up will be indicated as an off schedule visit.

Late Follow-up Reporting -

Late follow-up is required in at 3 and 6 months postoperative intervals, and annually postoperatively through at least 1 but no more than 8 years. For MVR patients enrolled greater than 60 days postoperatively, follow-up will be at 3-months post enrollment then annually on the anniversary of implant. This is also done on CRF3. Follow-up must be in person; telephone or questionnaire follow-up is not allowed. If a patient misses a scheduled follow-up visit, the investigator must make an effort to contact the patient to determine the reason for the missed visit. A new visit should be scheduled, but if the patient refuses to return for follow-up or otherwise cannot be

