contacted, the patient is then recorded as lost or withdrawn from the study. The efforts to maintain contact will be documented on the follow-up form, and every effort will be made to minimize the number of patients lost (zero being preferable). Thus, a follow-up form (CRF3) is due annually on each patient whether or not follow-up has occurred.

At the 3 month follow-up each patient shall be randomized into treatment group. The investigator will log into the data management system to be assigned the random (test or control) group for the patient per the web-based procedure briefly described below. If any patient has suffered a thrombotic or bleeding event during the initial 3 month period, he/she shall not be randomized into a group and shall be considered a screening failure and the event shall not be analyzed with any group under an intent-to-treat classification.

The randomization module implements a standard randomization algorithm, Marsenne Twister that is implemented in Java. (Matsumoto M. and Nishimura T., "Marsenne Twister: A 623-Dimensionally Equidistributed Uniform Pseudo-Random Number Generator", ACM Transactions on Modeling and Computer Simulation, 1998;8:3-30.) The patented randomization module can provide block and stratified randomization results.

The procedure automatically executes upon eligibility documentation for a study subject. The randomization result is presented on the screen instantaneously upon eligibility documentation using sponsor provided language and is also stored in the study database. The Tempo electronic randomization process ensures only eligible subjects are randomized and no errors are made in storing the correct result of randomization. The Tempo system audit trail documents the randomization results and time of execution.

Late follow-up information includes in all cases the patient initials or ID, cardiac rhythm, NYHA classification, and anticoagulant therapy information, including where applicable the most recent INR provided by the patient or QAS. For any new complication, the complication report (CRF4) must be completed and attached. All complications that have occurred between follow-up examinations must be reported on the form. Echocardiography per section III D is required at 1, 3 and 5 years.

Complication Reporting -

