Suture Interrupted Technique:	Suture Interrupted Pledgeted Everting Mattress Noneverting Technique: Continuous Other, specify:				
Crossclamp time:Minutes					
Cardioplegia:	$Cold$ \Box $Warm$ \Box Bo	th			
	Antegrade Retrograde	Both			
Intraoperative Drugs: Heparin □ Yes □ No					
Apro	$_{\rm otinin}$ \Box $_{\rm Yes}$ \Box $_{\rm No}$				
Intraoperative Adverse Events: Ves No (If Yes, complete below.)					
Prolonged Hypotension Yes N	o Difficulty Resta	arting Rhythm 🗌 Yes 🗌 No			
Excessive Bleeding \Box Yes \Box N	o Difficulty Wear	ning from Bypass \Box Yes \Box No			
Cardiac Tamponade 🛛 Yes 🖓 N	o Study Valve Ex	planted Yes No			
Cardiac Arrest $\Box_{\text{Yes}} \Box_{\text{N}}$	o Death	\square_{Yes} \square_{No}			
Other 🗆 Yes 🗆 M	lo If Yes, explain:				
Valve Orientation: Check the most accurate valve orientation description below based upon the direction of the valve axis. Mitral: Anatomical Other, describe:					
Aortic: LC/RC commissure RC/NC commissure NC/LC commissure					
Investigator Signature:	D	ate (m/d/y)://			

Institution:	MCRI On-X [®]	Patient Initials	
Investigator:	Anticoagulation Study CRF 3	Patient No.	
Visit Date (m/d/y)//	_ □ Early PostOpe	rative/Discharge	
	\Box Interim (3	or 6 month)	
	Annual (year) (12 + 2	month interval)
	└ Off Schedule		
Group: Randomized to: Treatm	nent Control		
Patient StatusImage: Missed Follow(If follow upImage: Lost to FollowOff Schedule)Efforts toImage: Missed FollowAdverse Event	ow Up Visit. Reason, ow Up: o Contact and Results: ent (Complete Complications I	Form CRF 4)	
Type of Examination: Office/Outpaties	nt 🗌 Hospital 🗌 Telephone	□ Other	
NYHA Class: I I II		Unknown	
Cardiac Rhythm:	Regular		
Atrial Fil	prillation Other, specify:		
Anticoagulant INone	U Warfarin/Cour	nadin	
	rel Heparin		
Aspirin	□ Other		
INR Blood Collec	tion Date (m/d/y):/	_/(closest to	date of visit)
New Complications: (Since last follow up) Yes No (C	omplete complicatio	n form, CRF 4)
Echo Completed (m/d/y)	Attach CRF 6 and send echo, a	pplicable only at 1, 2	3 and 5 yr follow-up.

Investigator Signature: _____ Date (m/d/y): ____/____

Institution:	MCRI On-X [®] Low Dose	Patient Initials	
Investigator:	Anticoagulation Study CRF 4		
	Complications 1 of 2	Patient No.	
Start Date (m/d/y)://	Stop Date (m/d/y):	or \	
Duration: Week	s Days Hours	Minutes	
Etiology:			
Complication Type (check all that apply)	Complicatio	on number:	
1. Thromboembolism INeurolo	gic: 🗌 TIA 🛛 Peripheral: 🗌] Major 🔲 Cardiac: MI 🗌 Unknown	
		Minor	

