7.1.2 Non-Date Values

Every effort will be made to obtain required data at each scheduled evaluation from all subjects who have been enrolled. There will be no imputation for missing data.

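### The plan has no step for finding vital status or primary events once a patient stops attending in person; events never learned of always favour a pass against the OPCs

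*Protocol*

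**What the plan says.** The in-person rule appears twice in Protocol III.C: in the opening text on Investigational Procedures ("visits should be made in person; telephone or questionnaire follow-up is not allowed") and under Late Follow-up Reporting ("Follow-up must be in person; telephone or questionnaire follow-up is not allowed").

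The steps after a missed visit are in Late Follow-up Reporting:

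- Contact is required, with one stated purpose: "the investigator must make an effort to contact the patient to determine the reason for the missed visit".
- A new visit is to be scheduled.
- The condition for leaving follow-up opens with "if the patient refuses to return for follow-up or otherwise cannot be" and closes with failed contact; the site then enters loss or withdrawal. The triggers are therefore refusal to return and failure of contact.
- The form is still owed: "a follow-up form (CRF3) is due annually on each patient whether or not follow-up has occurred". Efforts to keep contact are documented on it.

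CRF 3 (Protocol Appendix A) offers Office/Outpatient, Hospital, Telephone and Other as types of examination. Its patient-status block has entries for a missed visit with the reason, for loss with contact efforts and results, and for an adverse event with a pointer to CRF 4.

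Under Complication Reporting, all complications go on CRF 4. Serious or unexpected ones go to the monitor within 24 hours of the investigator learning of them. Neither duty depends on a visit.

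SAP 7.1.2 says of non-date values: "There will be no imputation for missing data". The SAP plans no sensitivity analysis for loss to follow-up.

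**The concern.** Thromboembolism, valve thrombosis, major bleeding, reoperation and death decide this trial, and some of them can themselves stop a patient attending. After the six-month and one-year visits follow-up is annual, so a site may first hear of an event treated elsewhere at the next visit. If the patient then refuses to come or cannot be reached, the site may record the loss without asking a relative, the treating physician or a hospital whether the patient is alive and event-free. A patient who has died or is in care elsewhere could well be one who cannot be contacted.

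For a patient who is reached but too ill to travel, the protocol requires a visit, bars telephone follow-up and names no alternative. CRF 3 suggests that telephone contact is acceptable. Sites have two conflicting instructions and may act differently.

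If loss is related to unrecorded events, censoring in the Kaplan-Meier analysis is informative and the linearized rates are too low. The OPC criterion compares a test-group rate with a fixed outside figure, so nothing offsets the shortfall. The Data Safety Monitoring Committee applies its termination rule (Protocol III.G) to the same rates.

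**Working it through.** **Inputs from the documents**

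- Comparison with control (Protocol II.D and Table 1): control 7.3%, test 6.0%, margin 1.5 percentage points, one-sided alpha 0.05, power 80%, 992 patient-years per group.
- OPC criterion (Protocol II.D): the null is R ≥ 2R_A for each event, with 95% confidence and 800 patient-years. The rates used are 0.8, 3.0 and 3.5% per valve-year. The row labels cannot be read in the copy reviewed; these three are taken as the primary events because 0.8 + 3.0 + 3.5 = 7.3.

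**Assumption.** A share f of events is never recorded. The documents give no value for f, so 5%, 10% and 20% are shown. Patient-years are held fixed, so f is best read as the proportional shortfall in the observed rate.

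**1. The plan's own figure.** With unpooled variance, n = (1.645 + 0.842)² × (0.073×0.927 + 0.060×0.940) / (0.015 + 0.013)² = 979. The Farrington-Manning method gives 992 exactly and reproduces all 24 rows of Table 1.

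**2. OPC criterion.** Let c be the largest count with P(X ≤ c | 2R_A × 800) ≤ 0.05, X Poisson. The false-pass chance when the true rate is exactly 2R_A is P(X ≤ c) at mean 2R_A × 800 × (1 − f). For R_A = 3.0% the mean is 48 and c = 36. With f = 5% the mean is 45.6, and with f = 10% it is 43.2.

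| R_A | Mean, c | f = 0 | 5% | 10% | 20% |
|---|---|---|---|---|---|
| 3.0% | 48, 36 | 4.4% | 8.5% | 15.4% | 38.9% |
| 3.5% | 56, 43 | 4.3% | 8.9% | 16.6% | 43.2% |
| 0.8% | 12.8, 6 | 2.9% | 4.2% | 6.0% | 11.6% |

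The direction is the same in every row. For the OPC of 3.0, f = 10% means about 5 events missed out of 48.

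**3. Comparison with control.** Put the true rates at the margin (7.3% and 8.8%) with 992 patient-years per arm. The false-pass chance is P(Z > 1.645 − (0.015 − d)/SE), where d is the observed test-minus-control difference and SE = √[(p_C(1−p_C) + p_T(1−p_T))/992] at the observed rates.

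At f = 10%:

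- Equal loss: rates 6.57% and 7.92%, d = 1.35 points, SE = 1.164 points. Shift = 0.15/1.164 = 0.129; false pass 6.5%. Poisson variance with 1000 patient-years gives 6.4%.
- Test arm only: rates 7.30% and 7.92%, d = 0.62, SE = 1.191. Shift = 0.88/1.191 = 0.739; false pass 18.3%.
- Control arm only: rates 6.57% and 8.80%, d = 2.23, SE = 1.195. Shift = −0.73/1.195 = −0.611; false pass 1.2%.

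At f = 5% these are 5.7%, 10.0% and 2.6%. At the planned rates (7.3% and 6.0%), equal loss of 10% leaves power at 80.6% against 80.5% with none missed. Loss of 10% in the control arm only cuts power to 60.1%.

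**The case against.** The best defence is that the ban concerns scheduled follow-up, not event reporting. Most of this stands:

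- A reader might infer that any patient who cannot travel must be recorded as lost. The text does not say so. Refusal and failure of contact are the triggers, and the patient who is reached but too ill to attend is a gap.
- A reader might infer that a stroke reported by telephone goes uncounted. It does not: once the site knows, the event belongs on CRF 4, and later censoring does not remove it.
- The protocol has other routes to capture. CRF 3 is due without a visit and prompts for adverse events. Cause of death must be established, with hospital reports attached when appropriate. Test patients with a thrombotic or bleeding event are still followed (III.F). Annual monitoring compares source records with reports (V). Patients unable to return are excluded at entry (II.B).
- A reader might infer that both criteria tilt toward a pass. That is certain only for the OPC criterion.
- The shares used above apply to all events, whereas the mechanism reaches only events the site never learns of. Many transient attacks and minor bleeds would not stop anyone attending. Nothing in the documents supports a share as high as 20%.
- The absence of imputation is not in itself a fault, since Kaplan-Meier analysis handles loss by censoring.

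What the defence leaves open is how the site learns of events. The 24-hour clock starts only when the investigator knows. For a missed visit, CRF 3 records the reason and contact efforts without requiring a search. III.F deals with events already known.

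**Conclusion.** The concern holds in a limited form. The in-person rule and CRF 3 conflict. Patients who are reached but too ill to attend are not provided for. In the text reviewed, no step establishes vital status or primary events once a patient refuses or cannot be contacted, and no sensitivity analysis covers the loss. Some pages are absent from the copy reviewed, so a procedure there cannot be excluded.

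Events never learned of always make the OPC criterion easier to pass. The effect can be material at modest shares: a nominal 5% test roughly doubles its error if 5% of events are missed, for the OPCs of 3.0 and 3.5. On the comparison with control the effect is modest if loss is equal in the two arms, strong toward a pass if it falls in the test arm, and against a pass if it falls in the control arm.

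All sizes rest on an assumed missed share, true rates at the null boundary, fixed patient-years and one-sided 0.05 as in Table 1. They show sensitivity and do not forecast bias.

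**What to change.** Reconcile both in-person statements in Protocol III.C with CRF 3, as follows:

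1. Keep in-person visits for NYHA class, rhythm and echocardiography.
2. When a visit is missed or refused, or the patient cannot travel, require the site to obtain vital status and the primary events (thromboembolism, valve thrombosis, bleeding, reoperation, explant, death). Acceptable sources are telephone, next of kin, the treating physician or hospital records, as consent allows.
3. Enter the source in the examination-type field of CRF 3 and report events on CRF 4.
4. Record a patient as lost only when all these sources fail, and censor at the last date on which event status is known.
5. Add to the SAP a sensitivity analysis for loss to follow-up, covering both the OPC criterion and the comparison with control, with unequal loss between arms among the scenarios.

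The cost is mainly wording and some site effort, because contact after a missed visit is already required and the CRF 3 boxes exist. Remote reports of minor bleeds will be less reliable; flagging the source lets the analysis examine them separately.
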